2. TRIAL OBJECTIVES AND ENDPOINTS

2.1 MAIN OBJECTIVES, PRIMARY AND SECONDARY ENDPOINTS

2.1.1 Main objectives

The main objectives of the trial are to demonstrate the effectiveness of BI 685509 and to characterize the dose-response relationship for BI 685509 in patients with DKD by assessing 3 doses and placebo.

2.1.2 Primary endpoint

Change from baseline in log transformed Urine Albumin Creatinine Ratio (UACR) measured in 10-hour urine after 20 weeks of trial treatment.

2.1.3 Secondary endpoints

Change from baseline in log transformed UACR measured in First Morning Void urine after 20 weeks of trial treatment.

Proportion of patients achieving UACR decreases in 10-hour urine of at least 20% from baseline after 20 weeks of trial treatment.

Proportion of patients achieving UACR decreases in First Morning Void urine of at least 20% from baseline after 20 weeks of trial treatment.

3. DESCRIPTION OF DESIGN AND TRIAL POPULATION

3.1 OVERALL TRIAL DESIGN

This trial is a multicentre, randomised, double-blind (within dose groups), parallel, placebo-controlled clinical trial to compare three doses of BI 685509 with placebo in patients with diabetic kidney disease who are on background treatment with either ACEi or ARB plus any other standard of care according to respective local guidelines.

A schematic illustration of the trial design is presented in [Figure 3.1: 1](#).

[figure not shown]

Figure 3.1: 1 Trial design

Patients will be enrolled (screened) in the trial once they have signed the informed consent. They will undergo a screening period of up to 3 weeks from the time of informed consent.

After their eligibility has been confirmed at screening, patients will continue in a 2-week baseline run in period. Patients who successfully complete the screening and baseline run-in period and meet the inclusion / exclusion criteria will be randomised equally into one of three parallel dose groups, and in each dose group to treatment either with BI 685509 or matching placebo in a 3:1 ratio (see [Figure 3.1: 1](#)).

From the start of the run-in until the end of the trial, at various time points patients will collect their urine for UACR sampling. These timepoints are listed in the [UACR and eGFR flow chart](#). For each day that UACR is collected patients will start by collecting a First Morning Void urine in the container provided. As soon as the First Morning Void sample is collected the clock starts for the 10-hour urine collection. During this 10-hour period every time the patient urinates, they collect their urine into the provided container. An aliquot of this urine will be taken and used as the 10-hour UACR sample.

Once at each time point of urine collection patients will also give blood samples for eGFR analysis. For each time point where a physical visit to the site is not foreseen, the patient will

be equipped with a [REDACTED] [REDACTED] kit to take blood at home, and urine collection containers to sample urine from their First Morning Voids and 10-hour collection container.

To decrease the burden on patients, where local regulations allow, samples taken at home between visits or when a home visit occurs will be shipped by the patient or a nurse or equivalent function visiting the patient for analysis at a central laboratory. Where this is not possible alternative arrangements will be made, e.g. samples taken to the investigational site.

After end of treatment patients will continue with a 4-week follow-up with further urine and blood sampling. Beyond analysis for safety, urine and blood samples in this trial will serve for biomarker analysis including UACR and eGFR.

The trial will be stratified according to SGLT2 inhibitor use and type of diabetes at the time of randomisation. SGLT2 inhibitors are a promising class of drugs for DKD patients and it is anticipated that their use might increasingly become standard of care. [P20-09106]. To avoid a confounding effect, treatment with SGLT2 inhibitors will have to be kept stable prior to trial participation and throughout trial treatment (see [section 4.2.2.1](#)). An approximate of 10% patients on Type 1 Diabetes Mellitus patients will be expected.

All patients will start on 1 mg TID BI 685509 or matching placebo. If the medication is tolerated, up-titration to 2 mg TID BI 685509 or matching placebo will occur after 2 weeks for patients in dose groups 2 and 3, and up-titration to 3 mg TID BI 685509 or matching placebo will occur after another 2 weeks for patients in dose group 3. Patients will receive 20 weeks of treatment in total, which is expected to be the duration required to obtain stable effects.

Following the 20-week treatment period, or at the time trial treatment is permanently discontinued, patients will have an End of Treatment (EoT) visit, which will be the start of a 4-week follow-up period. A first follow-up telephone call (FUp1) at least 7 days later is considered as the end of the Residual Effect Period (REP). Until the end of REP all AEs and changes to concomitant medication need to be collected, documented and reported.

During the entire follow-up period the patient will not be treated with trial medication, but should if possible continue with any background treatment they were on, and will collect additional urine and/or blood samples at home. At the end of the 4-week follow-up a last physical visit will occur where again blood and urine samples will be collected. Depending on local regulations and approvals this visit may occur at the site or the patient's home. With the conclusion of this visit the trial participation is complete for the individual patient. Historical serum creatinine data will be collected in the trial over a period of 3 years before start of treatment. This may be used in future to explore the benefit of BI 685509 in patients with rapid CKD progression.

Database lock will occur after the last patients have completed their final visit.

3.2 DISCUSSION OF TRIAL DESIGN, INCLUDING THE CHOICE OF CONTROL GROUP

A parallel group design was chosen to compare three different dose regimens, including a placebo control within each dose group, to find the optimal dose for phase III. Placebo control is used to control for observer and subject bias, and randomisation to control for assignment bias.

UACR was chosen as primary endpoint (10-hour collection) and secondary endpoint (responder rate and First Morning Void (FMV)) because it was shown in previous phase II trials by others in CKD that it is sensitive, differentiating different doses, broad in its dynamic range and reaching a stable plateau within a reasonable time after start of treatment. It has been accepted by authorities as dose finding biomarker in CKD. In the MRD phase I trial in patients (1366-0004) UACR in 10-hour urine collected over the day (approximately starting with the morning dose) showed a greater difference to placebo compared to FMV urine. It is considered that 10-hour urine is able to capture the drug effect during the dosing schedule, while FMV urine contains the urine produced over night. While a 10-hour urine at daytime may be easier for patient to collect, a 24-h collection would be more burdensome and prone to error during night time collection. Also 10-hour UACR may be superior to FMV urine as the latter is depending on many factors such as nocturia and time of the first urination in the morning.

Furthermore, the change in UACR upon treatment within approximately 16 weeks of full dose correlates with long-term patient relevant outcomes. Based on this and including a 4-week up-titration, until the target dose is achieved, the full duration of treatment has been selected to be 20 weeks. Since UACR is a parameter that varies intra-individually over time, multiple measurements are required at baseline and during the treatment period especially towards the end of treatment where a stable response to the drug should be achieved. Sequential collection of urine during a 4-week follow-up period may deliver exploratory results of response stability and potential rebound effects.

To further characterise haemodynamic effects and potential early benefit on renal function serum creatinine will be measured at regular intervals for exploratory analysis.

In this parallel design, double-blind conditions regarding the patient's treatment (active or placebo) are maintained within each dose group. It is not feasible to apply double-blind conditions between dose groups because the individual tablet strengths and matching placebo look different. Therefore investigators will know which dose group their patient is in but will be blinded to whether they are on active drug or placebo. Patients will be blinded to both the dose group they are on and whether they are taking active drug or placebo. Keeping investigators blinded to the dose group would require patients to take multiple tablets three times a day on top of the extensive background medication they already receive, which is considered too burdensome for this clinical trial. However, in order to minimise possible observer bias with regard to dose dependent effects, the dose group will be blinded to the patient as much as possible by applying the following measures:

The trial medication label will not include dose strengths so the dose will not be identifiable to the patient from the label.

Every effort should be made by the trial team and sites staff that the patient is not informed about the dose group assignment.

Up-titration or “pseudo-titration” will occur for all patients two weeks after start of trial medication and again after another two weeks, regardless of dose group (see [Table 4.1.4: 1](#)). Pseudo-titration is a term used to describe when patients are told that they are potentially assigned to a higher dose, but actually remain on the same dose:

- Patients in Dose Group 1 (1 mg TID) will be “pseudo-titrated” to 1 mg TID after two weeks and to 1 mg TID two weeks after that.
- Patients in Dose Group 2 (2 mg TID) will be up-titrated from 1 mg TID to 2 mg TID after two weeks and then “pseudo-titrated” to 2 mg TID two weeks after that.
- Patients in Dose Group 3 (3 mg TID) will be up-titrated from 1 mg TID to 2 mg TID after two weeks and to 3 mg TID two weeks after that.

However, in case the patient experiences a related adverse event or for any other reason the patient pauses trial treatment, the investigator will need to decide whether a down-titration is needed based on the rules reflected in [section 4.1.4](#) and the dose group the patient is assigned to. The patient will not know the specific rules. This will eliminate an additional burden of the patient to visit the site for a sham-downtitration if the patient is staying on the lowest dose already.

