[REDACTED]. A Drug-Drug Interaction (DDI) potential with CYP3A4 substrates cannot be excluded as BI 685509 is predicted to be a weak CYP3A4 inactivator. Inhibitors or inducers of UGT enzymes (especially UGT1A1) may potentially impact BI 685509 exposures in a clinically relevant manner. BI 685509 is a substrate of P-gp and OATP1B1/3 transporters. Co-administration of single doses of BI 685509 and the P-gp inhibitor itraconazole increased BI 685509 C_{max} approximately 1.35-fold and AUC_{0-tz} approximately 1.55-fold, which is considered not clinically relevant. OATP1B1/3 inhibition by rifampicin increased the exposure of BI 685509 after co-administration of single doses approximately 2.15-fold for C_{max} and 2.74-fold for AUC_{0-tz} , which is considered clinically relevant. Thus, OATP1B1/3 inhibitors will be restricted.

Residual Effect Period

The Residual Effect Period (REP) of BI 685509 is 7 days. This is the period after the last dose with measurable drug levels and/or pharmacodynamic effects still likely to be present.

Data from non-clinical studies

BI 685509 was evaluated in the rat ZSF1 model of diabetic nephropathy with once daily oral gavage dosing for 10 weeks on top of enalapril as a standard of care. This resulted in a dose-dependent reduction in urinary protein excretion (UPE) which was significant at ≥ 3 mg/kg and resulted in an additional $\geq 51\%$ inhibition of UPE beyond that achieved with enalapril monotherapy. At ≥ 10 mg/kg, BI 685509 significantly inhibited the incidence of glomerulosclerosis when compared to enalapril alone ($\geq 40\%$ vs. 8%). A 20% reduction in proteinuria beyond that produced by a clinically relevant dose of enalapril was achieved at 53 nM for BI 685509 based on PK/PD modelling analysis. Taking into account the differences in plasma protein binding between both ZSF1 rat and human, a projected $C_{max,ss}$ of 95 nM or an AUC_{ss} of 540 nM*h is required for efficacy.

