During a COVID-19 or similar pandemic, physical visits to the sites may need to be restricted to ensure patient safety. Based on a thorough assessment of the benefits and risks, the investigator may still decide to continue the trial treatment and trial medication may be shipped to the patient's home if acceptable according to local law and regulations (for more details see [section 6.2.1](#)). Shipment of trial medication to the patient's home will also be allowed to support regular visits performed at the patient's home.

Potential down-titrations (dose reductions) can be done based on the dose group known by the investigational site. This will be managed via the IRT system. Dose reductions must not be performed by instructing the patient to take less than the three daily doses. While the patient will not get to know the precise rules as listed in [sections 4.1.4.1](#) and [4.1.4.2](#), the patient will be informed that down-titrations may be needed as decided by the investigator.

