4.1.4.1 Rules for titration in case of interruption of trial treatment

Since an interruption of trial medication may have an influence on the tolerance, the following rules will apply for the safety of the patient:

An interruption of trial treatment is defined as any occurrence where 4 consecutive doses* or more were not administered (i.e. missed or dosing temporarily discontinued). **One dose refers to an individual timepoint e.g. morning dose, or middle dose or evening dose.*

- If less than 4 consecutive doses of trial medication are missed then the next dose of trial medication should be taken as scheduled.

After an interruption of trial treatment the patient should be restarted at 1 mg BI 685509/ placebo TID independent from the dose the patient was on before unless the patient was down-titrated due to an adverse event (see [section 4.1.4.2](#)) in which case:

- If they had been on 2 mg/3 mg BI 685509/ placebo they would re-start on 1 mg BI 685509/ placebo.
- If they had been on 1 mg BI 685509/ placebo then they should restart on placebo (matching 1 mg BI 685509).

Before any up-titration occurs the patient must have taken the preceding dose for at least 7 consecutive days. This applies throughout the treatment period.

- This may mean that a patient due to be up-titrated at Visit 4 or 5 (as per [Table 4.1.4: 1](#)) is held at their current dose until their next scheduled visit. They could also be up-titrated at an unscheduled visit once this requirement is met.

If interruption for any reason occurs after Visit 5, subsequent up-titration will be allowed either at a scheduled or unscheduled visits.

Patients with an interruption on 2 mg or 3 mg or matching placebo will need to return to the clinic either for the next scheduled or an unscheduled visit to receive 1 mg tablets before continuation of trial treatment.

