4.1.4.2 Rules for down-titration in case of intolerance to trial treatment

If a patient has an adverse event that the Investigator believes may be related to trial medication then the Investigator may either interrupt a patient's trial medication (re-start to follow the rules above (see [section 4.1.4.1](#)) or dose reduce the patient as described below. See [Appendix 10.3](#) for a schematic guidance on down-titration:

If the patient is on 1 mg TID or matching placebo the patient will be down-titrated to placebo matching 1 mg.

If the patient is on 2 mg TID or 3 mg TID (or corresponding matching placebo) and interrupts trial treatment

- less than 4 consecutive doses, then the patient will be down-titrated one level i.e.
 - 2 mg /placebo goes to 1 mg TID/ placebo.
 - 3 mg/ placebo goes to 2 mg TID/ placebo.
- 4 consecutive doses or more, then the patient will be down-titrated to 1 mg TID or placebo.

Dose-reduction must NOT be performed by taking less than the three daily doses or by splitting tablets so that a whole tablet isn't taken.

If the patient experiences a second adverse event that the Investigator believes is related and they have already had an interruption/ down-titration, then the patient should permanently discontinue trial treatment.

In case of persistent adverse events despite dose reduction, or severe effects at any dose, permanent treatment discontinuation should be considered.

Uptitration for patients who were down-titrated or interrupted for a related AE is not permitted.

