7.8.1 Adverse Events

Analyses of AEs will be descriptive in nature. All analyses of AEs will be based on the number of patients with AEs and NOT on the number of AEs.

Furthermore, for analysis of AE attributes such as duration, severity, etc. multiple AE occurrence data on the CRF, will be collapsed into AE episodes provided that all of the following applies:

- The same MedDRA lowest level term was reported for the occurrences
- The occurrences were time-overlapping or time-adjacent (time-adjacency of 2 occurrences is given if the second occurrence started on the same day or on the day after the end of the first occurrence)
- Treatment did not change between the onset of the occurrences OR treatment changed between the onset of the occurrences, but no deterioration was observed for the later occurrence

For further details on summarisation of AE data, please refer to "Analysis and presentation of adverse event data from Clinical Trials" [\(9\)](#) and "Handling of missing and incomplete AE da [\(4\)](#).

The analysis of AEs will be based on the concept of TEAEs. That means that all AEs occurring between first drug intake until 7 days after last drug intake will be assigned to the randomised treatment. All AEs occurring before first drug intake will be assigned to 'screening' and all AEs occurring after last drug intake + 7 days will be assigned to 'follow-up' (for listings only). AEs that start before first drug intake and deteriorate under treatment will also be considered as 'treatment-emergent'. For details on the treatment definition, see [Section 6.1](#).

If only the start date of an AE is collected (without start time), any AE occurrence on the same day as the first BI 685509 administration will be assigned to the on-treatment phase. AEs will also be summarised by the treatment at the onset of AE for any drug-related AE. In addition, a summary of patients with down-titration due to AE will be provided.

An overall summary of AEs will be presented.

Frequencies [N (%)] of patients with AEs will be summarised by dose group, primary system organ class, preferred term (using MedDRA), and intensity. Separate tables will be provided for patients with serious AEs (SAEs), patients with AEs of Special Interest (AESIs), patients with fatal AEs, and patients with discontinuations due to AEs.

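### Stepping down from the 1 mg level tells the investigator that the patient is now on placebo, contrary to Protocol 3.2, and the treatment-at-onset AE summary has no rule for events after that step

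*Protocol*

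**What the plan says.** **Blinding.** Protocol 3.2 says that double-blind conditions for the patient's "treatment (active or placebo) are maintained within each dose group". It explains that tablet strengths look different, so dose group cannot be concealed from the site. It then says: "Therefore investigators will know which dose group their patient is in but will be blinded to whether they are on active drug or placebo". Protocol 4.1.5.1 is narrower and promises blinding only to the randomised assignment within each dose group.

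**Down-titration.** Protocol 4.1.4.2 states: "If the patient is on 1 mg TID or matching placebo the patient will be down-titrated to placebo matching 1 mg". Protocol 4.1.4.1 has a restart rule with the same end point for the 1 mg level after down-titration for an AE. On who applies these rules, Protocol 4.1.4 says: "Potential down-titrations (dose reductions) can be done based on the dose group known by the investigational site". Sections 3.2 and 4.1.4 keep only the patient from knowing them.

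**AE analysis.** The main summaries are by randomised treatment (Protocol 7.2.5; SAP 6.1 and 7.8.1). The SAP adds: "AEs will also be summarised by the treatment at the onset of AE for any drug-related AE". Protocol 1.2 sets the residual effect period (REP) at 7 days and explains: "This is the period after the last dose with measurable drug levels and/or pharmacodynamic effects still likely to be present". SAP 6.1 counts the REP from the last administration of study drug. It also assigns AEs during an interruption to the randomised treatment and flags them in listings. Neither document says how an AE is classed after a switch from active drug to placebo.

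**The concern.** The 1 mg step has one possible outcome. An investigator who applies it knows what the patient takes next, which is what 3.2 says the investigator does not know.

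This matters for one output. The treatment-at-onset summary contains only AEs judged drug-related, and that judgement is the investigator's (Protocol 5.2.6.1.6). Two problems follow for events after the switch:

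- **Labelling.** An event that starts days after the last active dose is labelled placebo, although the sponsor's own REP says drug levels or effects are still likely.
- **Assessment.** Relatedness is judged with knowledge of placebo in these patients but blind in randomised placebo patients who have not stepped down. If both fall under one placebo label, the summary mixes two kinds of judgement.

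What is at stake is whether that summary can be interpreted, and whether 3.2 describes the blinding correctly.

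**Working it through.** No stated figure is at issue, so the check is mainly a cross-reading. The arithmetic only shows reach and why no net effect can be given.

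**1. Does the investigator know the current treatment?**

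| Needed | Source | Met? |
|---|---|---|
| Knows the dose group | Protocol 3.2, 4.1.4 | Yes |
| Knows the dose level | Titration schedule, Protocol 4.1.4 | Yes |
| Knows the rule | Protocol 4.1.4.2; withheld from the patient only | Yes |
| Rule has one outcome | Protocol 4.1.4.2: active and placebo both go to placebo | Yes |

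So current treatment is known from the step onwards. Because both arms move to placebo, the step says nothing about the randomised arm.

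**2. Who can reach this step?** The 3:1:3:1:3:1 allocation of 240 gives 60 active and 20 placebo in each dose group, or 180 active and 60 placebo. All 240 start at the 1 mg level for weeks 1 and 2. The 60 + 20 = 80 in Dose Group 1 stay there to week 20.

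**3. How many do?** The documents give no rate. Assuming that 5%, 10% or 20% of Dose Group 1 step down:

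- randomised to active: 60 × 0.05, 0.10, 0.20 = 3, 6, 12
- randomised to placebo: 20 × 0.05, 0.10, 0.20 = 1, 2, 4

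**4. Which way would the placebo figure move?** Three inputs are assumed: 10 patients switched from active drug are counted with the 60 randomised to placebo; 20% of the 60 (12 patients) have a drug-related AE; and x of the 10 have one after the switch. The figure is (12 + x)/(60 + 10):

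- x = 0: 12/70 = 17.1%
- x = 2: 14/70 = 20.0%
- x = 4: 16/70 = 22.9%

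Knowledge of placebo pushes x down and carry-over pushes it up. The figure can fall, stay at 20% or rise.

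**5. Does the 7-day window rest on half-life?** No. With the terminal half-life of 9 to 15 h (Protocol 1.2), the fraction left at 24 h would be 2^(−24/9) = 0.16 to 2^(−24/15) = 0.33. At day 7 with 15 h it would be 2^(−168/15), about 0.0004. Decline is biphasic, so the 24 h figures may be too high. The window rests on the sponsor's REP, which also covers pharmacodynamic effects.

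**The case against.** The strongest reply is that the blind that matters is intact. Section 4.1.5.1 protects the randomised assignment, and a step that treats both arms alike cannot reveal it. The AE that triggers the step is judged before it, and the patient remains blinded. All of this stands. A reader might infer that the allocation has been unblinded, and the documents do not support that. What fails is the statement in 3.2, which concerns what the patient is on.

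A second reply is that the affected output is minor. It is an additional descriptive summary restricted to drug-related AEs, and no safety testing is planned. In the main tables, events up to 7 days after the last study drug stay with the randomised arm. This also stands. A reader might go further and infer that known-placebo patients dilute the placebo rate and so distort dose selection. That does not follow, for three reasons:

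- Neither document defines the columns or denominators of this summary. Pooling with the 60 randomised placebo patients is an inference.
- The direction is open, as step 4 of the working shows.
- Protocol 7.2.2 and SAP 7.4.1 say only that safety is considered when choosing a dose. Neither names this table.

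A third reply is that exposure is limited. Under Protocol 4.1.4.2, a second related AE after an earlier interruption or down-titration ends treatment, so few drug-related events can accumulate after the switch. That is fair and limits the size. It does not settle how those events are labelled.

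Finally, a footnote and listing flag, as SAP 6.1 uses for interruptions, might be thought enough. That would disclose the issue but leave events within the REP under placebo.

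**Conclusion.** The point holds in a limited form. Protocol 3.2 is inconsistent with 4.1.4.1 and 4.1.4.2, and the passages must be reconciled. The investigator's blinding to current treatment ends at the step from 1 mg to placebo; blinding to the randomised arm does not.

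On the plain reading of treatment at onset, the supplementary summary then labels REP events as placebo and combines aware with blinded relatedness judgements. Its size cannot be stated, since the number of patients stepping down is not given, and its net direction is unknown. The main AE tables by randomised treatment are unaffected. The correction is worth making because it is specific and cheap, not because a material distortion has been shown.

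The conclusion assumes that the rule is applied as printed and that treatment at onset means the treatment being taken when the event starts. It takes no position on the down-titration rule itself.

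**What to change.** **SAP 6.1 and 7.8.1, treatment-at-onset summary only:**

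- Attribute AEs with onset within the 7-day REP of the last active dose to that active dose.
- Show later AEs in a separate category, for example 'placebo after down-titration (investigator aware)'. Patients randomised to placebo who take the same step enter this category from the switch, as they have no active dose.
- Keep this category apart from randomised placebo before any switch.
- Add a footnote that relatedness after the switch, including during the 7 days, was judged by an investigator aware of the current treatment. The date rule corrects the label but not that awareness.

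**Protocol 3.2:** reconcile with 4.1.4.1 and 4.1.4.2 by stating that the investigator's blinding to current treatment, but not to the randomised arm, ends at this step.

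**Cost:** one extra category, one date rule and a footnote in a supplementary table, plus one sentence in the protocol. Down-titrations are managed through the IRT (Protocol 4.1.4), so the switch should be traceable without new data collection. The new column will be small and can support description only.
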